Patients who complete the Pre-Operative visit, but do not receive treatment with the study device will be considered discontinued. The Patient Discontinuation case report form will indicate proposed surgery not performed.

Patients have a right to withdraw permission (revoke informed consent authorization). Patients who withdraw consent will have no further private health information collected. Once authorization is revoked, patients may no longer participate in the research activities, but standard medical care will not be affected. Revoking authorization only affects information obtained after the request has been received, but not information obtained prior to that time. Patient withdrawal will be documented on the Patient Discontinuation case report form.

Remuneration will be provided to all subjects who complete scheduled follow-up office assessments at 24 months and annual follow-up visits thereafter as required. The subjects' financial compensation package will be outlined in the Informed Consent Form and approved by the Institutional Review Board (IRB) prior to the start of the study.

Every attempt will be made to contact patients who are non-compliant or lost to follow-up. Three contact attempts by certified letters will be documented. Patients who are lost to follow-up will be documented on the Patient Discontinuation case report form.

To compensate for a potential 20% attrition rate, additional subjects have been added to the sample size. The number of enrolled and completed subjects will be closely monitored, and if needed patients will be added to assure the study endpoints can be achieved.

K. Data Collection

The purpose of the case report form is to reconstruct the study. Information should always be documented in the source document first, and then transferred to the case report form, either paper or electronic. As an exception, the Oswestry Disability Index (ODI) and Patient Assessment forms are considered source documents. It is recommended that patient questionnaires be completed prior to the patient meeting with any clinical staff to minimize the bias in the study or in accordance with site specific standard operating procedures.

Patient confidentiality will be protected at all times and patient identifiers will be used.

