Case report forms must be completed in black ink. To correct an entry, strike a single line through the error and mark the correct response. Date and initial the correction. Do not use liquid paper or correction tape.

Case report forms should be submitted via an electronic data capture system within 15 days of evaluation. Radiographs should be sent via Fed Ex to Zimmer Spine, Clinical Affairs, [name] within two weeks of evaluation.

V. STATISTICAL ANALYSIS

A. Analysis Population

The population for analysis will include all subjects who have completed eligibility screening, signed an informed consent, and have met inclusion and exclusion requirements.

A poolability analysis will be done to ensure that the two Dynesys devices (*Dynesys/Dynesys Top Loading* with autograft at the instrumented levels and *Zimmer DTO Implant* with autograft at the instrumented levels) have similar outcomes. The summary statistics resulting from the primary safety and fusion endpoints, for each subgroup, will be explored to assess possible differences in results based on the subgroup. Additionally, poolability will be assessed by comparing the subgroup population characteristics for key baseline, demographic and clinical characteristics as well as for primary diagnoses. If there are no differences in this comparison, the subgroups will be pooled for the purpose of analysis.

Similarly, a poolability analysis will be done to ensure that there are no differences in outcomes between the different level procedures (1-level, 2-level, 3-level). The summary statistics resulting from the primary safety and fusion endpoints, for each subgroup, will be explored to assess possible differences in results between the subgroups. Additionally, poolability will be assessed by comparing the sub group population characteristics for key baseline, demographic and clinical

characteristics as well as for primary diagnoses. If there are no differences in these comparisons, the subgroups will be pooled for the purpose of analysis.

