A meta-analysis was done using the same methodology as was used for the primary endpoint, fusion rate. When sufficient data were available for baseline characteristics, point estimates and 95% confidence intervals were generated for use to assess comparability of baseline data in the historical literature to the experimental data. The data were extracted from the same literature that was used to obtain an estimate for the primary endpoint of fusion rate. The first table below represents the detail available for use in comparison of the treatment group to the literature control data for the baseline characteristics and the second table contains the point estimates of interest for the baseline characteristics from the literature. Comparability will be inferred if the rates of males or smoking status in the experimental group are contained in the respective 95% confidence intervals established using the literature control rates. Comparability for age will be inferred if the point estimate for mean age in the experimental group is contained in the range presented for the historical control. Additionally, a frequency distribution of pre-operative diagnoses, from both the experimental group and what is available in the literature control group will be done to ensure comparability between the data from each.

Point Estimates Demographic Endpoints					
Age	Mean	STD	MIN	MAX	
Weighted Average	55.9706	NA	40.72783	75.31652	
Random Effects	Rate	SE	LCL	UCL	
Gender (Male)	35.78%	3.14%	28.78%	42.77%	
Smoking Status	39.11%	7.13%	21.64%	56.57%	
BMI - not enough information					

Demographic Endpoints	N	Age	Gender (% Male)	Smoking Status (%)	BMI
Acharya 2008	22	55	36.4%		
Chen 2005*	74	61.6	20.3%		
Cheng 2009	66	48	52.9%	0.221	
Christensen 2002	63	46	41.3%	0.65	
Christensen 2002	71	45.5	37.0%		
Dimar 2006	45	52.7	44.4%	0.222	
Fernandez-Fairen_1 2007	41	61.42	35.7%		
Glassman 2008	52	69.9	32.7%	0.173	28.1 +/-6.1
Lee 2009	182	59	33.5%		
Moller 2000	37	39	43.2%	0.57	
Thalgott_1 1997	21	55		0.429	
Thalgott_2 1997	21	45		0.523	
Wang 1998	94	67.03	17.0%		

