To assure that baseline characteristics of the history control data are similar to those found in the experimental data, the demographic characteristics from the study data will be reviewed to confirm that the characteristics of age, gender, smoking status, and preoperative diagnosis in the test data are similar to the data that existed for the historical control data. The rate of males and rate of smokers will be checked against the 95% confidence interval found in the point estimate table. The distribution of preoperative diagnoses will be tested for no difference between the historical control and the test group. The average age will be checked to assure that it is in the range from 41 to 75. If any differences are noted, patients with extreme data will be removed until the rates and means of the test population do reside within the bounds determined by the meta-analysis. If needed, more patients will be enrolled in the test group to assure that the sample size is sufficient for inferential testing.

B. Primary Analysis: Fusion Status

Fusion success will be defined as evidence of bridging bone and angulation of <5° and translation of <3mm at treated levels at 24 months. Radiographic assessment will determine for each patient a fusion status, either fused or not fused. The primary endpoint is fusion status at Month 24. Efficacy will be confirmed by the achievement of fusion in the experimental group when compared to the rate established in a literature control. Normand (1999) provided the direction for the meta-analysis¹. The details of that analysis included creating population mean and variance estimates using a weight of the inverse of the variance. (See pp. 335-336 for complete description of the algorithm) A point estimate of 80.6% with a standard error of 2.6% was established. The 95% confidence interval for this point estimate is (75.0%, 86.3%).

If Month 24 fusion status cannot be determined, but fusion was determined to have occurred earlier, the Month 24 status will be considered fused. Otherwise, subjects without earlier fusion who are missing Month 24 values will be excluded from primary analysis.

For the purpose of a sensitivity analyses, all subjects excluded as described above for a missing Month 24 fusion status will be defined as not fused.

C. Primary Analysis: Safety Endpoints and Evaluation

Subjects will be clinically evaluated for adverse experiences and functional outcomes over the course of 24 months.

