Detailed and descriptive analyses will be provided for all adverse events, including specific treatment required and outcomes for all secondary surgeries at the index and adjacent levels, any deaths, and all potential device related adverse events. Adverse event incidence rates, severities and time course will be determined. For subsequent surgical procedures, at every treated level, the type of surgical procedure required the incidence rate and time course will be determined and reported.

¹ Normand, S. T. (1999). Tutorial in biostatistics meta-analysis: Formulating, evaluating, combining, and reporting. *Statist. Med.* (18), 321-359.

All of the safety endpoints will be summarized descriptively at all available assessments. Summaries will be chosen as appropriate for the scale and distribution of the measures being analyzed. For categorical variables, summaries will consist of counts and percentages to describe the distribution of the endpoint. For continuous variables, descriptive summaries will consist of N, Mean, Median, Standard Deviation, Minimum and Maximum. Similarly, exact incidence and rates of AEs and subsequent surgical procedures will be calculated for the experimental group and whenever possible for the control group.

Assessing adverse events (AEs) using only the literature control data is not sufficient, because of the heterogeneity of reporting across the manuscripts. Thus, we propose using the observed data from the recent Dynesys IDE clinical study (historical). The AEs collected in this study (historical) is expected to have a similar profile as those in the present study (experimental). A test for non-inferiority will be performed using both incidence and rates, for each AE category, in both the historical control and experimental group. Non-inferiority will be inferred if the lower limit of the 95% confidence interval around the treatment difference between the 2 groups is greater than $\delta = -10\%$, using the hypotheses below where p_e is the incidence or rate in the experimental group and p_d is the incidence or rate in the historical study group.

$$H_0: p_e - p_d \leq -0.10$$
$$H_1: p_e - p_d > -0.10$$

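### Eligible patients are to be removed until baseline rates match the literature, with no rule for who, when or blind to outcome, and no untrimmed Month 24 fusion analysis is planned

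*Combined protocol and SAP*

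**What the plan says.** Section V.A (Analysis Population) opens with an inclusive definition: "The population for analysis will include all subjects who have completed eligibility screening, signed an informed consent, and have met inclusion and exclusion requirements". Later in V.A the plan compares the study sample with the literature. For sex and smoking, "Comparability will be inferred if the rates of males or smoking status in the experimental group are contained in the respective 95% confidence intervals", which are 28.78% to 42.77% men and 21.64% to 56.57% smokers. Mean age must lie between 41 and 75. For diagnosis, "The distribution of preoperative diagnoses will be tested for no difference between the historical control and the test group"; no bound is tabulated.

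If any difference is found, "patients with extreme data will be removed until the rates and means of the test population do reside within the bounds determined by the meta-analysis", and "If needed, more patients will be enrolled in the test group to assure that the sample size is sufficient for inferential testing".

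Section V.B plans one sensitivity analysis of the primary endpoint. It counts as not fused the subjects left out because Month 24 status is missing. It does not bring back subjects removed for baseline mismatch. V.D covers fusion at other time points.

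**The concern.** The two parts of V.A cannot both define the primary set once a difference appears, and the removal rule does not identify patients.

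- **Who.** No patient is extreme for sex. The Clinician Evaluation form records packs per day and years of smoking, but the rule uses only the proportion of smokers and does not say that exposure decides who goes.
- **How many.** For sex or smoking alone the bound fixes the count. If both miss, the count depends on who is removed and in what order. For diagnosis there is no bound to stop at.
- **When, and with what knowledge.** Neither is stated. V.A has fusion summaries explored by subgroup for poolability, the Imaging Protocol (III.C) sends films for review every six months, and interim reports are issued. The plan does not say that removal follows a look at outcomes, but nothing prevents it.

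In a single-arm comparison with a literature rate, the analysed set determines the result. If removal leans towards unfused patients, even unintentionally, the fusion rate rises, and a reader could not tell whether this had happened.

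**Working it through.** **Plan's own figures.** The sample size reproduces as a two-sided one-sample test of 0.806 against 0.706: n = [(1.96√(0.806×0.194) + 0.8416√(0.706×0.294))/0.10]² = 134.2 (stated: 134), and 134/0.8 = 167.5, so 168. These are not in dispute; 134 is used below as the evaluable number.

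**What the bounds are.** Sex: (42.77 − 35.78)/3.14 = 2.23 SE. Smoking: (56.57 − 39.11)/7.13 = 2.45 SE. These are confidence intervals for a pooled mean, not a range in which one comparable study should fall. In the V.A table, 5 of the 11 cohorts with a sex figure are outside (17.0, 20.3, 43.2, 44.4 and 52.9%), as are 3 of the 7 with a smoking figure (17.3, 57 and 65%).

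**Chance of a trigger on sex or smoking, n = 134.**
- No between-study variance (exact binomial at 35.78% and 39.11%): 1 − 0.914 × 1.000 = 0.09.
- New study exchangeable with the literature cohorts (an assumption), between-study variances 0.0069 and 0.0298, which reproduce the plan's SEs: 1 − 0.55 × 0.675 = 0.63.
- The same with DerSimonian-Laird variances 0.0099 and 0.0389: 1 − 0.49 × 0.613 = 0.70.

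**Number removed (assumed mixes, n = 134).**
- 60 men (45%): remove 5, giving 55/129 = 42.6%.
- 67 men (50%): remove 17, giving 50/117 = 42.7%.
- 27 smokers (20%): remove 10 non-smokers, giving 27/124 = 21.8%.
- 20 smokers (15%): remove 42 non-smokers, giving 20/92 = 21.7%.
- 50% men and 15% smokers together (10 male and 10 female smokers, 57 male and 57 female non-smokers): the minimum is 42, for example 28 male and 14 female non-smokers, leaving 39/92 = 42.4% men and 20/92 = 21.7% smokers. Random one-at-a-time removal has median 56 (sex first, 95% range 47 to 70) or 58 (smoking first, 47 to 72).

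**Chance of passing at a true rate of 70.6%.** Pass if p̂ − 0.806 − 1.96√(p̂(1 − p̂)/n + s²) > −0.10. Here s = 0 treats the comparator as fixed; figures in brackets use s = 0.026, since V.B says "A point estimate of 80.6% with a standard error of 2.6% was established". Patients leave the over-represented group by a hypergeometric draw (blind) or a Fisher noncentral hypergeometric draw with unfused patients at odds 2 or 3. With no removal the chance is 2.8% (1.0%).

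| Removed | Blind | Odds 2 | Odds 3 |
|---|---|---|---|
| 5 men | 3.2% (1.2%) | 4.3% (1.7%) | 5.2% (2.1%) |
| 10 non-smokers | 3.6% (1.3%) | 6.5% (2.6%) | 9.1% (4.0%) |
| 17 men | 3.3% (1.1%) | 7.3% (2.9%) | 11.2% (4.9%) |
| 42 non-smokers | 3.9% (2.2%) | 19% (13%) | 38% (28%) |

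If unfused men always go first, removing 17 gives 72% (57%).

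**One case by hand.** With 95 of 134 fused (70.9%), the lower limit of the difference is −0.097 − 1.96 × 0.0392 = −0.174, a fail. Remove 17 unfused men: 95/117 = 81.2%, lower limit 0.006 − 1.96 × 0.0361 = −0.065, a pass. With s = 0.026 it is 0.006 − 1.96 × 0.0445 = −0.081, still a pass.

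**Power at a true 80.6%, no replacement.** 78% (64%) at n = 134, 75% (58%) at 117 and 68% (58%) at 92.

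**The case against.** Several points on the other side carry weight.

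- **The size depends on assumptions.** The sample mixes and the odds of 2 and 3 are not from the documents. With the literature SE included, removing 5 men leaves the error at 1.7% to 2.1%, below 2.5%; only the 42-removal case is large. Against blind removal of the same number (fixed comparator), the ratios are about 1.4 to 1.6 for 5 men and 5 to 10 for 42 non-smokers, rather than 1.5 to 1.9 and 7 to 14 against no removal. This stands as a caution on size. No removal is still the natural reference, because it is the state after the fix.
- **The 63% to 70% trigger needs exchangeability.** The study enrols only degenerative spondylolisthesis or pseudarthrosis, and the documents give no literature diagnosis mix. This also stands; the figure without between-study variance is 9%.
- **Diagnosis may have a stop.** A non-significant test could serve, or diagnosis may not drive removal at all, since the sentence names only rates and means. The text supports either reading, which is itself a reason to rewrite it.
- **Outcome access is indirect.** The image reviewers have no role in choosing the set, and replacement enrolment suggests removal near the end of enrolment, before many Month 24 visits. That timing is inferred, and earlier fusion readings would already exist.
- **Some fusion summaries may be untrimmed.** The objective of reporting fusion at every treated level is not tied to the trimmed set. But no untrimmed Month 24 non-inferiority analysis is specified.
- **A pre-specified, outcome-blind rule would also work.** It would close the route to bias, but would still discard eligible patients to meet bounds that several source cohorts fail.

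**Conclusion.** The concern holds, and this must be fixed. Followed as written, V.A yields a primary fusion set chosen by discretion whenever sex, smoking or diagnosis departs from the literature; the wide age range is unlikely to matter. The conflict with the inclusive population definition and the absence of an untrimmed Month 24 analysis rest on the text alone.

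The size is conditional. If removal ignores outcome, the loss is mainly power and representativeness. If it favours unfused patients, the false-claim rate rises from slightly to severely, depending on how many are removed and how strongly selection follows outcome. Safety is less affected: V.C already says "Detailed and descriptive analyses will be provided for all adverse events", so only the denominators of the safety non-inferiority tests are unclear.

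**What to change.** In V.A, delete the removal sentence and the replacement-enrolment sentence tied to it. The separate attrition provision in IV.J ("if needed patients will be added to assure the study endpoints can be achieved") can stay. State that the primary fusion analysis includes every eligible treated patient, subject only to the V.B rule for missing Month 24 status, and that the safety non-inferiority tests use all of them. Report sex, smoking, age and diagnosis beside the literature descriptively.

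As a sensitivity analysis only, rake the fusion rate to the marginal literature rates of 35.78% men and 39.11% smokers. State that the joint distribution is not available and that the targets are themselves uncertain (smoking 21.64% to 56.57%). Diagnosis can only be described, because no literature mix is given.

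The cost is SAP wording and one extra analysis. Imbalance is then reported rather than removed, and weighting loses precision. With effective n = (Σw)²/Σw², 134 patients become about 124 at 50% men, 110 at 20% smokers, 92 at 15% smokers, and 85 at 50% men and 15% smokers together (assuming independence). That last figure runs from about 120 to 52 as the smoking target moves from the lower to the upper end of its interval.

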- *Operative/Discharge Evaluation*: dates of admission, surgery and discharge, operative level, estimated blood loss, duration of surgery, discharge medications, device implant specifics, reason for device choice, autograft harvest and placement and neurological assessment
- *Adverse Event (as needed)*: record events, device relationship, date of complication, severity, outcome and treatment details
- *Protocol Deviation (as needed)*: deviation and reason
- *Patient Discontinuation (as needed)*: reason for discontinuation and date

C. Post-Operative – 6 month (+/- 4 weeks)

The following procedures and assessments will be performed following surgery.

- *Patient Assessment*: pain level and satisfaction
- *Oswestry Disability Index (ODI)*: functional assessment
- *Clinician Evaluation*: neurological assessment (sensory and motor testing, reflex testing and straight leg raising), medication usage, employment status, tobacco use and surgical results
- *Radiographs*: A/P, N/L, flexion, extension
- *Radiographic Assessment*: overall and unilateral fusion success (translation motion <3mm, angulation motion <5° and bridging bone) will be assessed by site radiologist and an independent reviewer
- *Adverse Event (as needed)*: record events, device relationship, date of complication, severity, outcome and treatment details

- *Protocol Deviation* (as needed): deviation and reason
- *Patient Discontinuation* (as needed): reason for discontinuation and date

D. Post-Operative – 12, 24 month (+/- 8 weeks)

The following procedures and assessments will be performed following surgery.

- *Patient Assessment*: pain level and satisfaction
- *Oswestry Disability Index (ODI)*: functional assessment
- *Clinician Evaluation*: neurological assessment (sensory and motor testing, reflex testing and straight leg raising), medication usage, employment status, tobacco use and surgical results
- *Radiographs*: A/P, N/L, flexion, extension
- *Radiographic Assessment*: overall and unilateral fusion success (translation motion <3mm, angulation motion <5° and bridging bone) will be assessed by site radiologist and an independent reviewer
- *Adverse Event (as needed)*: record events, device relationship, date of complication, severity, outcome and treatment details
- *Protocol Deviation* (as needed): deviation and reason
- *Patient Discontinuation* (as needed): reason for discontinuation and date

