- **Removal:** a procedure where the entire original system configuration is removed with/without replacement.*
- **Reoperation:** any surgical procedure at the involved level(s) that does not involve removal, modification or addition of any components to the system.
- **Supplemental Fixation:** a procedure in which additional instrumentation not under study in the protocol is implanted at the spine level(s) under study.

* Elective removals following fusion are not considered adverse events; however, they will still be reported.

All adverse events observed during the course of this study, regardless of severity or relationship to the investigational device will be recorded on the Adverse Event case report form. All events should be followed until resolved or until a chronic, stable state is achieved.

All serious adverse events and unanticipated adverse device effects or events of unexpected severity must be reported to Zimmer Spine within 24 hours of the time the investigator learns of the event or effect. Zimmer Spine will notify the reviewing IRBs within 10 days of the time of learning of the event.

H. Adverse Events Advisory Group

Independent spine surgeons (neuro or orthopedic) will be selected from a subset of 13 member (10 US and 3 OUS) Zimmer Spine Clinical Affairs Advisory Group (CAAG), who are not study investigators, to determine adverse event severity and device relationship.

The CAAG surgeons serve two-year terms and function to provide expert advice to the Clinical Affairs department with respect to protocol development, unmet clinical needs, clinical benefits of devices, quantification and measurement of clinical evaluations, pathology, diagnosis and indication and review of explant cases during clinical trials. The surgeons have a strong core competency in the conduct and logistics of clinical trials. This group allows Zimmer Spine the ability to quickly and responsibly respond to any questions regarding clinical use of our devices, review of data from clinical trials and response to other research collaborators with respect to study conduct. The members of this panel can be trained on the protocol, most importantly, with respect to the blind adjudication of adverse events determining severity and relatedness. The depth of the panel allows

Zimmer Spine to easily convene three members for adjudication and receive expert assistance in review of any adverse events that may ultimately be “unanticipated” or “serious.”

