Removal and Refusion				

E. Baseline and Operative Analysis

Baseline summaries will be chosen to be appropriate for the scale and distribution of the measures being analyzed. Statistical methods will be the same as described above for the non primary endpoint analyses.

F. Missing data

Except for the primary analysis, if a value, at any assessment is not available for analysis, it will be excluded from summaries.

G. Study Hypothesis and Sample Size Determination using a Literature Control

Study Hypothesis

The hypothesis is Dynesys fusion rate is non-inferior to the historical literature sample data estimated fusion rate of 80.6%. This hypothesis will be assessed by testing that the difference between the experimental rate (p_e) and the historical control rate (p_c) is not worse than 10%. The non-inferiority test will be inferred if the lower limit of the 95% confidence interval around the **treatment difference** between 2 groups is greater than $\delta = -10\%$.

$$H_0: p_e - p_c \leq -0.10$$

$$H_1: p_e - p_c > -0.10$$

Sample Size

Sample size for the Dynesys Post-Market Surveillance Study was estimated using SAS, Proc Power with a testing level alpha (Type I) error level of 0.05, 80 percent statistical power, a meaningful difference of 10%, and a success rate for lumbar fusion from the literature historical

control group of 80.6% (0.806). For this set of criteria, the sample size was 134, without adjustment for attrition. With a 20% attrition sample added, this would result in a sample size of 168.

Sample size estimates are presented in Table 2.

Table 2: Proposed Sample Sizes

Primary Endpoint	Difference	Predicted Success	Type I Error	Power	N Patients
Radiographic Success (Fusion)	10%	80.6%	0.05	80%	168

VI. TIMELINE

A. Clinical Trial Agreement

No portion of this protocol will be implemented until both copies of the Clinical Trial Agreement have been completed by both parties.

Table 3: Study Timeline

Study Timeline	Sponsor Expectation
Expected date of Study Initiation	March 2012
Expected date of first IRB Approval(s)	January 2012
Expected monthly number of sites obtaining IRB approval	1
Expected subject enrollment initiation	March 2012
Expected average number of subjects to be enrolled/month	7
Expected Date of Subject Enrollment Completion	March 2014
Expected date of Subject follow-up Completion	March 2016
Reports	
Interim Postmarket Surveillance Study Report	Every 6 months through 2 years, annually thereafter

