Bony Bridging will be graded as "Absent, Present or Unclear" in accordance with the definitions provided below. Bridging will be defined as a continuous connection of mineralized tissue from the superior to the inferior vertebral body.

Absent: Absence of continuous bridging bone from endplate to endplate

Present: Presence of continuous bridging bone from endplate to endplate

Unclear: No determination or absence or presence of continuous bone bridging can be made based on the provided radiographs

There is no scientific consensus concerning the minimum threshold of bridging required to classify a level as solidly bridged. Therefore, discretion will be left to the radiologist to determine whether sufficient bridging exists to render an affirmative assessment.

E. Fusion Status

Fusion Status will be graded as 'Fused or Not Fused'. Fusion Status will be derived from a logical analysis of the following factors: bony bridging, angular motion and translational motion.

Not Fused: No evidence of bridging bone between the involved vertebral endplates and $\geq 5^\circ$ total angular motion and ≥ 3 mm translational motion

Fused: Evidence of bridging bone between the involved vertebral endplates and $<5^\circ$ total angular motion and <3 mm translational motion

Fusion Status will be reported for each treated level.

F. Other Radiographic Observations

Additional incidental observations or noteworthy findings will be documented at the radiologist's discretion and may include observations of screw/device loosening, lucency, malplacement or broken. Additional observations of spondylolysis, retrolistesis, degeneration, fracture and arthrodesis will be identified. Clarifying remarks regarding the assessments will also be provided, including the location/type of failure/condition.

Dynesys® Spinal System and the Zimmer® DTO™ Implant Instructions for Use

Important information for the operating surgeon

Zimmer GmbH
P.O. Box
[name]
[contact]
[contact]
www.zimmer.com

Manufacturer:
Zimmer GmbH
[name]
[name]

Distributed in the USA by:
Zimmer Spine, Inc.
[name]
[name]
[contact]
[contact]
[contact]

Art. No. D011 500 217 - e - Ed. 10/09

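### A patient without a Month 24 fusion status can enter the primary analysis only as fused, which biases the fusion rate upward under plausible missingness, by an amount the plan's figures cannot fix

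*Combined protocol and SAP*

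**What the plan says.** The primary endpoint is fusion status, fused or not fused, at Month 24 (V.B). For a patient without one, V.B gives two rules. The first is: "If Month 24 fusion status cannot be determined, but fusion was determined to have occurred earlier, the Month 24 status will be considered fused". Under the second, "subjects without earlier fusion who are missing Month 24 values will be excluded from primary analysis". Nothing carries an earlier not-fused reading forward. A sensitivity analysis follows, in which "all subjects excluded as described above for a missing Month 24 fusion status will be defined as not fused". Patients carried forward as fused stay fused in it, and the plan does not say what it decides.

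Earlier readings will exist: at 6 and 12 months fusion "will be assessed by site radiologist and an independent reviewer" (IV.C, IV.D). A missing status need not mean a missed visit. The Imaging Protocol (V.D) allows a bridging grade of Unclear, meaning "No determination or absence or presence of continuous bone bridging can be made based on the provided radiographs", so a patient who attends may also have no determinable status.

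On numbers, IV.J says "To compensate for a potential 20% attrition rate, additional subjects have been added to the sample size", and V.G says "With a 20% attrition sample added, this would result in a sample size of 168". Neither section gives an expected share missing Month 24 or an expected early fusion rate.

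**The concern.** The two rules treat missing patients unequally. Those read fused at 6 or 12 months stay in the numerator and denominator. Those read not fused, and those with no earlier film, leave both. Selecting the known successes from among the missing raises the rate unless something offsets it. The study has one arm and an external benchmark, so no concurrent group is subject to the same rule. The error therefore passes directly into the non-inferiority comparison, in the device's favour.

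**Working it through.** **Inputs from the documents.** Benchmark 80.6%, standard error 2.6% (V.B). Margin 10 points, so the null boundary is 70.6% (V.G). Size 134 before attrition and 168 after (V.G). A potential 20% attrition (IV.J).

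**Assumed, because the documents do not give them.** m, the share missing Month 24: 20% (the attrition allowance) and 10%. q, the share of missing patients read fused earlier: 10% to 60%. Patients lost before any post-operative film have q = 0. p is the true Month 24 rate.

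**The plan's own figures.** 134/0.8 = 167.5, rounded up to 168. The 134 reproduces as a two-sided one-sample test of 80.6% against 70.6%: [1.96·√(0.806·0.194) + 0.8416·√(0.706·0.294)]²/0.10² = 134.2.

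**Bias when missingness is unrelated to outcome.** The expected primary rate is [(1−m)p + mq]/[(1−m) + mq], so

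bias = m·q·(1−p)/[(1−m) + m·q].

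This is positive whenever m and q exceed 0 and p is below 1. It does not require any fusion to be lost. With m = 20%, p = 70.6% and q = 30%, 134.4 patients are observed (94.9 fused), 10.1 are added as fused and 23.5 are dropped. The expected rate is 105.0/144.5 = 72.7%, a bias of +2.1 points.

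**Bias when missingness depends only on the earlier reading and fusion persists.** Let f be the share fused early, s the later fusion rate in the others, and r the missing share in the others. The true rate is f + (1−f)s. The plan estimates [f + (1−f)(1−r)s]/[f + (1−f)(1−r)]. This gives the early-fused group too much weight, so it is too high whenever r is above 0 and s is below 1. Suppose early-fused patients skip Month 24 twice as often, with 20% missing overall and a true rate of 70.6%. For f = 10%, 30% and 60% the plan's bias is +0.6, +1.5 and +2.3 points. Using observed Month 24 values only gives −0.7, −1.7 and −2.8.

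**Effect on the test (N = 168, m = 20%, nominal one-sided 2.5%).** With the SE carried, a pass requires (rate − 0.806) − 1.96·√[rate(1−rate)/n + 0.026²] > −0.10. With a fixed benchmark, the 0.026² term is dropped (Wald).

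| q | Bias at 70.6% / 80.6% (points) | False pass, SE carried | False pass, fixed Wald | Sensitivity analysis passes, true rate 70.6% / 80.6% (fixed Wald) |
|---|---|---|---|---|
| 10% | +0.7 / +0.5 | 2.0% | 4.8% | 0.0% / 0.1% |
| 30% | +2.1 / +1.4 | 4.2% | 9.8% | 0.0% / 2.8% |
| 60% | +3.8 / +2.5 | 10.5% | 22% | 0.7% / 43% |

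Observed-only gives 1.3% (SE carried) and 3.3% (fixed Wald). At 10% missing, false passes for q = 10% to 60% are 1.4% to 3.5% (SE carried) or 4.1% to 9.1% (fixed Wald). There the sensitivity analysis passes at most 1.5% at the null.

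**When the direction reverses.** If observed patients fuse at 70.6% and m = 20%, the plan's estimate is too low only if fusion among the missing exceeds [plan estimate − (1−m)p]/m. That is 74%, 81% and 90% at q = 10%, 30% and 60%.

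**The case against.** There are four fair objections.

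First, carrying fusion forward has a rationale. If early-fused patients tend to skip Month 24, observed-only analysis is biased downward by a similar or larger amount. This stands, and it is why simply dropping every missing patient is not the remedy. It does not rescue the plan, because the bias comes from excluding the other missing patients rather than from believing the early fusions.

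Second, the same section already contains a stress test. At the null with 20% missing it passes at most about 0.7% of the time, so nearly every false primary pass would sit beside a failed sensitivity result. At 10% missing and q = 60% it passes 1.5% of the time, against 9.1% for the primary. A reader might infer that the plan has no protection, and that is not so. But the same analysis passes a device truly at 80.6% only about 3% of the time at q = 30%, and 43% at q = 60%, with 20% missing. A failure therefore cannot separate a false pass from a sound one, and the plan does not say how a disagreement would be read.

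Third, a reader might infer a false-positive rate of around 22%. The documents do not support that as a finding. It needs q = 60%, 20% missing, an error-free benchmark and a Wald interval. V.G asks for an interval around a difference between two groups and V.B gives the benchmark a standard error, so the range with that error carried is the fairer one to lead with. Part of the fixed-benchmark excess belongs to the interval itself: observed-only is already 3.3%.

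Fourth, IV.J plans repeated certified letters, payment for completing the 24-month visit, and added patients if needed. The first two may keep m low. Adding patients does not remove bias.

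**Conclusion.** The rule in V.B is one-sided and should be changed. The upward direction holds if missingness is unrelated to outcome, or depends only on the earlier reading with fusion persisting. It is not universal: it reverses if missing patients fuse sufficiently more often than the others, so the documents do not support saying that the rate must be overstated.

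The size is unknown, since q and the Month 24 missing share are not given and 20% is only an allowance. With 168 patients, 20% missing, a true rate of 70.6% and q from 10% to 60%, the bias is +0.7 to +3.8 points. False non-inferiority is about 2% to 10.5% with the benchmark's error carried, or 4.8% to 22% with a fixed benchmark and Wald interval. At low q or 10% missing there is little or no excess once that error is carried. The sensitivity analysis exposes the problem but does not settle the claim.

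**What to change.** In V.B, replace the one-way rule with multiple imputation of every missing Month 24 status, stratified by the 6- and 12-month fusion reading. State its assumption: missingness depends only on the variables in the model. Add number of levels and smoking only with a method that handles perfect prediction, because if fusion is permanent every observed early-fused patient is fused at Month 24. Annual readings after Month 24 (IV.E) may inform the imputation where available.

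Report two supporting analyses: observed Month 24 only, noting its downward bias if early-fused patients skip the visit, and the plan's present carry-forward rule. Keep missing-as-not-fused as the stress test. State in advance that the imputation result governs, and how a disagreement will be reported.

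Imputation stratified by earlier reading was checked by simulation at 20% missing (20,000 trials, 30 imputations, fixed benchmark). False non-inferiority was about 3% and bias was within 0.2 points. The check assumed permanent fusion and missingness that depends only on that reading, so it does not test the fuller model or a failure of the assumption.

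The cost is SAP wording and modest programming on data already collected. The reported rate would be lower by about 0.5 to 3.8 points in the cases above. Power at a true 80.6% (fixed benchmark, Wald, 20% missing) would be about 79% to 85%, near the planned 80%, rather than the 85% to 97% that the present rule appears to give.
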